3.8.2 Off-Study Criteria

- Completed 2-year follow-up period
- Participant request to be withdrawn from the study
- Lost to follow-up
- Death
- Screen failure
- There is significant participant noncompliance
- The investigators decide to end the study
- The investigator's discretion

3.8.3 Lost to Follow-up

A participant will be considered lost to follow-up if he or she fails to return for 3 scheduled visits and is unable to be contacted by the study site staff.

The following actions must be taken if a participant fails to return to the clinic for a required study visit:

- The site will attempt to contact the participant and reschedule the missed visit within one month and counsel the participant on the importance of maintaining the assigned visit schedule and ascertain if the participant wishes to and/or should continue in the study.
- Before a participant is deemed lost to follow-up, the investigator or designee will make every effort to regain contact with the participant (where possible, 3 telephone calls and, if necessary, an IRB approved certified letter to the participant's last known mailing address or local equivalent methods). These contact attempts should be documented in the participant's medical record or study file.
- Should the participant continue to be unreachable, he or she will be considered to have withdrawn from the study with a primary reason of lost to follow-up.

4 CONCOMITANT MEDICATIONS/MEASURES

4.1 SYSTEMIC IMMUNOSUPPRESSIVE THERAPY

Participants will be advised to contact the study team before starting any new medications.

4.1.1 Concomitant Systemic Immunosuppression

At enrollment, many subjects will be receiving some immunosuppressive medications that were used to prevent or treat acute GvHD. The dose of these medications must have been stable for 2 weeks. Subjects may continue on stable doses of their immunosuppressive medications with the intent to taper it. Immunosuppression taper may be initiated after 4 weeks on the study treatment. Steroids should be tapered by approximately 20% every 2 weeks. Addition of any new systemic immunosuppressive therapy aimed at controlling chronic GvHD symptoms is prohibited and will be considered treatment failure.

Use of steroids for treatment of adrenal insufficiency will be discussed with PI.

4.1.2 Steroid Pulse for Chronic GvHD Flare

One steroid pulse (prednisone equivalent of 0.5-2 mg/kg/day) is allowed for clinical disease control and stabilization during the first 4 weeks after starting ibrutinib. In case of classic chronic GVHD typical maximal corticosteroid dose for a pulse would be 1mg/kg/day prednisone or equivalent as per usual standard of care. Chronic GVHD manifestations which present simultaneously with acute GVHD signs (chronic GVHD overlap) may require higher doses pulse (up to 2/mg/kg/day) as per usual standard of care. Determination for needing a corticosteroids pulse will be made by the primary practicing clinician and/or PI who will jointly make decision that such intervention would be beneficial to the participant. Subjects may remain on the corticosteroid pulse for up to 2 weeks after which they will begin a taper with the intent of decreasing back to the enrollment steroid dose within 4-6 weeks. More rapid tapering schedule is permitted if clinically appropriate. Rounding of corticosteroid doses is acceptable.

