Abbreviated Title: Ibrutinib for Chronic GvHD

Version Date: 4/26/2023

Abbreviated Title: Ibrutinib for Chronic GvHD

NIH Protocol #: 20C0058

Version Date: 4/26/2023

NCT Number: NCT04294641

Title: A Study of Front Line Ibrutinib without Corticosteroids for Newly Diagnosed Chronic Graft-versus-Host Disease

NIH Principal Investigator: [name]
Immune Deficiency Cellular Therapy Program
National Cancer Institute, Center for Cancer Research
[name]
[contact]
Email: [contact]

Drug Name:	Ibrutinib
IND Number:	146697
Sponsor:	Center for Cancer Research
Manufacturer:	Pharmacyclics LLC
Supplier	Pharmacyclics LLC

Commercial Agents: None

COORDINATING CENTER: NCI

SAFETY MONITORING COMMITTEE (SMC): NCI INTRAMURAL SMC

PRÉCIS

Background:

- Chronic graft-versus-host disease (GvHD) is the leading cause of late morbidity and non-relapse mortality following allogeneic hematopoietic stem cell transplantation (alloHSCT), occurring in 40-60% long-term survivors.
- Chronic GvHD occurs due to the dysfunctional peripheral tolerance during post-transplant hematopoietic reconstitution that allows the development and persistence of alloreactive donor-derived T and B cells.
- Prednisone is the front-line therapy; however, about 50% of participants have steroid-refractory disease and there is no standard second-line therapy.
- The most attractive approach for controlling chronic GvHD would be early therapy intervention which could prevent the most severe and irreversible clinical manifestations.
- Anti-B-cell therapy delivered early in chronic GvHD could be effective and steroid-sparing.
- Ibrutinib, reversible small molecule inhibitor of Bruton's tyrosine kinase, has been shown to be well-tolerated and effective in phase 1b/2 trial for steroid refractory chronic GvHD.

Objective:

- To evaluate efficacy of ibrutinib as a first-line treatment for persons with newly diagnosed chronic GvHD by measuring the overall response rate (complete response [CR] + partial response [PR]) at 6 months, according to the 2014 NIH Consensus Criteria

Eligibility:

- Newly diagnosed, moderate or severe chronic GvHD according to the 2014 NIH Consensus Criteria, requiring systemic immunosuppression
- Age \geq 18 years old
- Karnofsky performance status \geq 60%
- History of prior alloHSCT; any donors, conditioning regimens and graft sources are allowed
- Adequate cardiac, hepatic and other organ function
- Adequate laboratory parameters

Design:

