1.2.3 Study Rationale

For more than three decades the most widely used first-line systemic therapy of chronic GvHD has been prednisone alone or in conjunction with calcineurin inhibitors (cyclosporine([52](#)) or tacrolimus [TAC]); however, this approach has a durable response rate of less than 50%.

Currently there is no FDA-approved therapy for newly diagnosed chronic GvHD and development of well-designed prospective and innovative therapeutic studies is an urgent unmet clinical need.

In this study we propose the use of ibrutinib as the front-line therapy for newly diagnosed chronic GvHD, instead of high-dose steroids. Our central hypothesis is that ibrutinib will be effective and well tolerated as a single agent, front-line systemic therapy for newly diagnosed chronic GvHD.

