6.3.1 Response Criteria

Efficacy will be assessed using NIH consensus criteria measuring for therapeutic response in clinical trials for chronic GvHD. The calculations for CR, PR and progressive disease are provided in [Appendix H](#).

- **CR** is defined as complete resolution in all of signs and symptoms at all affected organs or tissues.
- **PR** is defined as improvement in ≥ 1 organ or tissue with no progression in any other affected organ or tissue.
- **Stable Disease (SD)** is defined as no change in chronic GvHD.
- **Flare** is defined as exacerbation of chronic GvHD manifestations during withdrawal of immunosuppressive therapy which do not exceed those at the beginning of the trial and improves after reinstatement of previous treatment. For the purpose of this study, any flare which requires change or intensification of systemic therapy beyond the one per protocol allowed steroid pulse within initial four weeks will be considered a therapy failure.
- **Progressive disease (PD)** is defined as failure of therapy to control chronic GvHD. Participants who progress prior to 6 months evaluation will be also evaluable for the primary efficacy endpoint.
- **Mixed response** is defined as an improvement in some organs but worsening in others and will be categorized as progressive disease.

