10.2 SAMPLE SIZE DETERMINATION

The primary objective of this trial is to determine the overall response rate of ibrutinib as a first-line treatment for subjects with newly diagnosed chronic GvHD based on the response at or before 6 months, according to the 2014 NIH Consensus Criteria. In similar subjects who ordinarily would receive steroid treatment, the clinical response rate using NIH criteria may typically be on the order of 30-40%. The goal would be to determine if using ibrutinib would rule out a 20% response rate and target a rate of 45%. For these subjects, the trial will be conducted using an optimal two-stage phase II trial design (Simon R, Controlled Clinical Trials 10:1-10, 1989) in order to rule out an unacceptably low PR+CR rate of 20% ($p_0=0.20$) in favor of an improved response rate of 45% ($p_1=0.45$). With $\alpha=0.10$ (probability of accepting a poor treatment=0.10) and $\beta = 0.10$ (probability of rejecting a good treatment=0.10), this first stage will enroll 14 evaluable subjects, and if 0 to 3 of the 14 have a clinical response, then no further subjects will be accrued. If 4 or more of the first 14 subjects have a response, then accrual would continue until a total of 25 evaluable subjects have been enrolled. As it may take 3 to 6 months to determine if a subject has experienced a response, a temporary pause in the accrual may be necessary to ensure that enrollment to the second stage is warranted. If there are 4 to 7 subjects with a response out of 25 subjects, this would be an uninterestingly low response rate. If there were 8 or more of 25 (32%) who experienced a response, this would be sufficiently interesting to warrant further study in later trials. Under the null hypothesis (20% response rate), the probability of early termination is 69.8%.

It is expected that approximately 1-2 subjects per month may enroll on this trial; thus, it is anticipated that 1.5 to 2 years may be required for accrual of up to 25 evaluable subjects. In order to allow for up to 3 inevaluable subjects and screen failures (screening will occur on this protocol), the accrual ceiling will be set at 40 (3 for inevaluable participants and 12 for screen failures).

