10.4.7 Subgroup analyses

None are intended.

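### The primary rate counts responses after the allowed steroid pulse like any other and no analysis separates them, so alone it does not support single-agent or without-corticosteroids wording

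*Combined protocol and SAP*

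**What the plan says.** The protocol is titled "A Study of Front Line Ibrutinib without Corticosteroids for Newly Diagnosed Chronic Graft-versus-Host Disease". Section 1.2.3 proposes ibrutinib in place of high-dose steroids and states the central hypothesis that "ibrutinib will be effective and well tolerated as a single agent".

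On steroids, section 4.1.2 provides: "One steroid pulse (prednisone equivalent of 0.5-2 mg/kg/day) is allowed for clinical disease control and stabilization", within the first 4 weeks of ibrutinib. The pulse may be held for up to 2 weeks and is then tapered "with the intent of decreasing back to the enrollment steroid dose within 4-6 weeks". The same section gives 1 mg/kg/day as the typical maximum in classic disease and up to 2 mg/kg/day for overlap disease. Exclusion criterion 2.1.2.3 and section 4.1.1 also let participants enter on steroids of up to 0.5 mg/kg/day and continue them with the intent to taper.

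Sections 3.1 and 4.1.1 treat added systemic immunosuppression for chronic GvHD as treatment failure. The pulse is the exception: under section 6.3.1, change or intensification of systemic therapy for a flare "beyond the one per protocol allowed steroid pulse within initial four weeks will be considered a therapy failure".

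The primary analysis (10.4.2) is the fraction of evaluable participants with a response, with 80% and 95% confidence intervals. Pulse use plays no part in it. The need for pulses and the ability to taper steroids are exploratory objectives (1.1.2, 10.1.3, 10.4.9) and are not tied to response. On subgroup analyses, section 10.4.7 says "None are intended".

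**The concern.** The pulse uses the class of drug that ibrutinib is meant to replace, and section 10.2 credits steroid treatment with a response rate of about 30-40%. A participant who is pulsed in the first month and reaches CR or PR is a full responder. With one arm and no split by pulse, nothing in the planned analysis shows how many responses occurred without added steroids.

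What is at stake is the wording of the conclusion. The rate answers a question about a strategy: ibrutinib first, with one early pulse if needed. The title and central hypothesis ask about ibrutinib without that help. Reading the first as the second would probably overstate the single-agent effect.

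**Working it through.** **Inputs from section 10.2.** p0 = 0.20, p1 = 0.45; stop if 3 or fewer of 14 respond; positive if 8 or more of 25 respond; steroid response rate 30-40%.

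**The plan's own figures.** With X1 ~ Bin(14, p) and X2 ~ Bin(11, p):

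- P(early stop) = P(X1 ≤ 3). At p = 0.20 this is 0.698, matching the stated 69.8%.
- P(go) = Σ over x = 4 to 14 of P(X1 = x) · P(X2 ≥ 8 − x). At p = 0.20 this is 0.093 and at p = 0.45 it is 0.903. Both design limits of 0.10 are met.

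The design arithmetic is sound. The question is what a counted response means.

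**Timing.** Read the 4-week window as limiting when the pulse may start, and cycles as 28 days:

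- Latest intended return to the enrolment dose: 28 + 14 + 42 = day 84.
- 6-week visit, C2D15: 28 + 15 = day 43.
- 3-month visit, C4D1: 3 × 28 + 1 = day 85.
- 6-month visit, C7D1: 6 × 28 + 1 = day 169, which is 169 − 84 = 85 days (about 12 weeks) after the latest intended return.

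A response taken strictly at month 6 is thus well clear of the pulse. However, section 10.2 describes the primary objective as "based on the response at or before 6 months", while sections 1.1.1 and 10.1.1 place it at 6 months. Under the section 10.2 wording, a response seen at day 43 or day 85, during or just after a late pulse and taper, could count. The pulse also returns to the enrolment dose, not to zero.

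**Illustration of size.** The documents give no pulse uptake, so let f be an assumed uptake. Assume a true rate of 0.20 without a pulse and s = 0.30 to 0.40 with one, borrowing the section 10.2 steroid figure. Then p = 0.20(1 − f) + s·f:

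| Uptake f | Apparent rate p | P(go) |
|---|---|---|
| 0 | 0.20 | 0.093 |
| 10% | 0.21-0.22 | 0.117-0.143 |
| 25% | 0.225-0.25 | 0.157-0.239 |
| 50% | 0.25-0.30 | 0.239-0.438 |

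**The opposite convention.** Suppose every pulsed participant counted as a non-responder and the rate otherwise were 0.45. Then p = 0.45(1 − f), and the same rule gives:

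| Uptake f | p | P(go) |
|---|---|---|
| 0 | 0.45 | 0.903 |
| 10% | 0.405 | 0.811 |
| 25% | 0.3375 | 0.591 |
| 50% | 0.225 | 0.157 |

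That convention is useful as a lower bound and unsuitable as a decision rule.

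**The case against.** The other side has several good points.

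- **Safeguards exist.** Under 3.1, 4.1.1 and 6.3.1, a response that needs steroids intensified again later is a failure. Most endpoint statements say 6 months, about 12 weeks after the latest intended end of the pulse, and 4.1.2 permits a faster taper. This stands and limits carry-over. It does not exclude a remission begun under the pulse, and it weakens if the section 10.2 timing applies.
- **The size is assumed.** The 30-40% refers to patients who would ordinarily receive steroid treatment, so applying it in full to a pulse of up to 2 weeks is generous. Pulses go to participants who need disease control and may do worse. This stands: the table shows sensitivity and is not an estimate.
- **The strategy is legitimate.** The primary objective speaks of first-line treatment, and the decision is only whether further study is warranted. This also stands, which is why the primary endpoint and go rule need no change.

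A reader might infer that the primary result is invalid, that the real false-positive rate is 0.24 or 0.44, or that section 10.4.7 forbids any look at pulse use. The documents support none of these. The design meets its error limits for the rate it counts, uptake is not given, and pulse use is already an exploratory objective; what is missing is a link to response. Nor do they support resting every single-agent statement on the pulse-as-failure rate alone, which would swap an uncertain upward bias for a potentially severe downward one.

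**Conclusion.** The point holds as a matter of what the primary rate estimates. As planned, the rate is for ibrutinib with one optional early steroid pulse on background immunosuppression. Alone, it does not support the title's wording or the single-agent hypothesis.

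For that wording the direction of bias is plausibly upward and the size is unknown. If uptake is 10%, the illustrative change in P(go) is small (0.093 to 0.12-0.14); at 25% it is material (0.16-0.24). Both ranges rest on the assumed uptake, a 20% rate without a pulse and the full 30-40% rate with one. The go/no-go arithmetic is unaffected. This should be corrected before analysis, because a split by pulse chosen after the results are seen would carry little weight in a single-arm trial of 25 participants.

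**What to change.** Leave treatment, the primary endpoint and the go rule unchanged. In section 10.4.2:

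1. State that the primary rate is for ibrutinib with the one allowed early pulse.
2. Pre-specify three supportive analyses:
   - (a) the number pulsed, and 6-month CR+PR by pulse yes/no, descriptive and noted as confounded by indication;
   - (b) 6-month CR+PR with pulse recipients counted as non-responders, labelled a conservative lower bound;
   - (c) among responders, prednisone-equivalent dose at 6 months relative to enrolment.
3. Require any single-agent or steroid-free statement to cite these results beside the primary rate.

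Also reconcile the endpoint timing in 1.1.1 and 10.1.1 with that in 10.2, so that a response seen only during the pulse or taper does not count by default.

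The cost is analysis-plan wording: section 6.1 already requires all medications to be recorded. The drawbacks are small, confounded groups and a lower-bound rate that may fall well below the primary rate.

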4.2 TOPICAL IMMUNOSUPPRESSIVE THERAPY

Subjects may remain on topical immunosuppressive or symptomatic therapy for chronic GvHD. Addition of new topical immunosuppressive or symptomatic therapy is allowed per NIH Chronic GvHD Ancillary and Supportive Care Working Group standard guidelines, however each such topical intervention must be carefully recorded and reported.

4.3 ANCILLARY THERAPY AND SUPPORTIVE CARE

Ancillary therapy and supportive care for chronic GvHD is permitted and recommended as outlined in the NIH Consensus Development Project 2014 Ancillary Therapy and Supportive Care Working Group Report. Use of topical or organ specific medications to treat or prevent bronchiolitis obliterans (e.g., inhaled steroids/azithromycin/montelukast) or GI acute GvHD (e.g., budesonide or beclomethasone) will not be considered systemic treatment for chronic GvHD; however, each such organ specific or topical intervention must be carefully recorded and reported in the final study data report.

Use of neutrophil growth factors (e.g., filgrastim and pegfilgrastim) or red blood cell growth factors (erythropoietin) is permitted per institutional policy. Transfusions may be given in accordance with institutional policy.

Infection is the most common cause of mortality in participants with chronic GVHD and infection prophylaxis requires special emphasis. The immune defects in chronic GVHD are broad, encompassing macrophage function, antibody production, and T cell function. Prevention, early diagnosis, and prompt treatment of infections are essential to the supportive care of participants with chronic GVHD. Infection disease prevention and management guidelines will be according the NIH Consensus Development Project 2014 Ancillary Therapy and Supportive Care Working Group Report and can be modified by the respective institutional guidelines.

While standard guidelines for aspergillosis prophylaxis in participants on ibrutinib do not exist, we will implement following generally recommended strategy in this protocol:

- a) If participant is on more than 0.20 mg/kg prednisone equivalent per day we recommend receiving isavuconazole (or an alternate agent) prophylaxis;
- b) If participant is on single agent ibrutinib or lower doses of steroids than 0.20 mg/kg prednisone equivalent +/- any other immunosuppressive agent, the decision will be left to the clinician based on the clinical risk assessment in a given participant.

Clinical vigilance for invasive fungal infections will be pursued in all participants. We recommend checking serum galactomannan at scheduled clinic visits and exert low threshold for imaging studies and early BAL when suspicion exists. We also recommend checking trough isavuconazole levels at each visit if feasible or at least couple times earlier at the protocol driven follow up appointments.

4.4 MEDICATION TO BE USED WITH CAUTION

4.4.1 CYP3A Enzyme Inhibitors/Inducers

Ibrutinib is metabolized primarily by CYP3A4.

A list of common CYP3A inhibitors and inducers is provided in [Appendix C](#). For further information, please refer to the current version of the ibrutinib IB and examples of inhibitors, inducers, and substrates can be found at <http://medicine.iupui.edu/clinpharm/ddis/main-table/>. This website is continually revised and should be checked frequently for updates. Avoid concomitant use of strong CYP3A inducers ([Appendix C](#)). Consider alternative agents with less CYP3A induction and transition to a new agent within 4 weeks of study treatment initiation. Dose modifications for participants on CYP3A4 inhibitors are listed in Section [3.2.1](#).

Avoid grapefruit and Seville oranges during ibrutinib treatment, as these contain moderate inhibitors of CYP3A.

4.4.2 Antiplatelet Agents and Anticoagulants

Use ibrutinib with caution in subjects requiring anticoagulants or medications that inhibit platelet function. In an in vitro platelet function study, inhibitory effects of ibrutinib on collagen induced platelet aggregation were observed.

Supplements such as fish oil and vitamin E preparations are recommended to be avoided during treatment with ibrutinib.

Bleeding events of any grade, including bruising and petechiae, occurred in subjects treated with ibrutinib. Subjects with congenital bleeding diathesis have not been studied. Ibrutinib should be

held at least 3 to 7 days pre- and post-surgery depending upon the type of surgery and the risk of bleeding (see Section [4.6](#)).

Subjects requiring the initiation of therapeutic anticoagulation therapy (e.g., atrial fibrillation) should be monitored closely for signs and symptoms of bleeding and the risks and benefits of continuing ibrutinib treatment should be considered.

4.4.3 Drugs That May Have Their Plasma Concentrations Altered by Ibrutinib

In vitro studies indicated that ibrutinib is not a substrate of P-glycoprotein (P-gp) but is a mild inhibitor. Ibrutinib is not expected to have systemic drug-drug interactions with P-gp substrates. However, it cannot be excluded that ibrutinib could inhibit intestinal P-gp after a therapeutic dose. There is no clinical data available. Therefore, to avoid a potential interaction in the GI tract, narrow therapeutic range P-gp substrates such as digoxin, should be taken at least 6 hours before or after ibrutinib.

4.5 PROHIBITED CONCOMITANT MEDICATIONS

Use of other investigational agents, chemotherapy, biologic or immunotherapy is prohibited during participation in this study.

